5.3 DOSE REGIMEN.....	19
5.4 TREATMENT COMPLIANCE.....	20
6. STUDY MEASUREMENTS	21
6.1 ULCER ASSESSMENT	21
6.2 PHYSICAL EXAMINATION AND VITAL SIGNS.....	21
6.3 LABORATORY EXAMINATION	21
6.4 STANDARD-OF-CARE PROCEDURES	22
7. STUDY SCHEDULE	23
7.1 SCREENING VISIT	23
7.2 INITIAL PHASE VISIT (ONLY FOR APPLICABLE SUBJECTS)	24
7.3 RANDOMIZATION VISIT	24
7.4 EVALUATION VISITS DURING TREATMENT PERIOD IN VISITS 4 TO 11	24
7.5 FOLLOW-UP VISITS	25
7.6 FINAL VISIT.....	25
8. ADVERSE EVENTS.....	26
8.1 DEFINITIONS	26
8.2 AE/SAE INTENSITY AND RELATIONSHIP ASSIGNMENT	26
8.3 COLLECTING, RECORDING AND REPORTING OF ADVERSE EVENTS	28
9. DATA ANALYSIS	29
9.1 DATA QUALITY ASSURANCE	29
9.2 CLINICAL DATA MANAGEMENT.....	29

10. SAMPLE SIZE AND STATISTICAL METHODS	30
10.1 DETERMINATION OF SAMPLE SIZE	30
10.2 STATISTICAL AND ANALYTICAL PLANS	30
11. ETHICAL CONSIDERATIONS	32
11.1 INFORMED CONSENT	32
11.2 IRB REVIEW	32
11.3 CONFIDENTIALITY OF DATA AND PATIENT RECORDS	32
12. PUBLICATIONS	34
13. RETENTION OF TRIAL DOCUMENTS.....	34
14. REFERENCES	35

PROTOCOL SUMMARY

Full Title	A Randomized, Double-Blind, Vehicle-controlled, Parallel, Phase II Study to Evaluate Efficacy and Safety of CSTC1 in Patient with Diabetic Foot Ulcers
Short Title	CSTC1 for Diabetic Foot Ulcers Phase II Study
Project No	CSCT1-01
Study Phase	Phase II
Sponsor	Charsire Biotechnology Corp.
Objectives	To evaluate the efficacy and safety of CSTC1 in patient with diabetic foot ulcers
Study Design	Randomized, double-blind, vehicle-controlled, multiple center, parallel study
Study Population	Subject aged at least 20 years old in Taiwan diagnosed with diabetic ulcer (which is selected by investigator and defined as the target ulcer) on the foot that not healing for at least 4 weeks
Number of Subjects	The sample size is determined to be 80 versus 20 subjects (4:1 ratio) for Treatment versus Control groups, 100 subjects in total. To ensure the completion of 100 evaluable subjects, around 125 subjects will be recruited.
Study Product, Dose, Route, Regimen	CSTC1 [REDACTED] [REDACTED] topical application, 2 times daily
Duration of Administration	12 weeks of treatment or confirmed complete ulcer closure, whichever comes first, and up to 12 weeks of post-treatment follow-up for subject with confirmed complete ulcer closure after at most 12 weeks of treatment; Subjects failed to achieve complete ulcer closure will be arranged for 4 weeks of safety follow-up

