3. Net change from baseline in laboratory test results (include hemoglobin, hematocrit, RBC, platelet, WBC with differential counts, HbA1c, fasting glucose, AST, ALT, creatinine and BUN)
4. Net change from baseline in vital signs

Statistical Analysis Analysis population

Three data sets will be introduced for statistical analysis.

Intent-to-treat (ITT) population:

- All randomized subjects who have received at least one dose study medication.

Per-protocol (PP) population:

- A subset of ITT population
- Fulfill all inclusion and exclusion criteria
- Dosed with at least 8 weeks study drug or with early confirmed complete ulcer closure AND with at least 70% treatment compliance
- Did not receive any prohibited treatment during treatment period
- With any post-treatment assessment relevant to efficacy endpoint up to end of dosing period

Efficacy endpoints will be analyzed on ITT and PP population.

Demographics, baseline characteristics, and safety endpoints will be analyzed on ITT population. Conclusion of efficacy will be made according to the result of ITT population analysis.

Analysis

Demographics and baseline characteristics will be summarized for each group by using descriptive statistics.

The efficacy endpoints will compare the CSTC1 group with vehicle group. Incidence of ulcer closure and ulcer closure rate at endpoint will be analyzed with Cochran-Mantel-Haenszel test (CMH test). Ulcer closure time will be estimated by using Kaplan-Meier methods and compared between groups by using log-rank test. Percentage change in ulcer size will be analyzed by using Analysis of variance (ANOVA) model with treatment group and center as factors. Further efficacy analyses with ankle brachial index (ABI) (<0.7 or not) as stratification may be performed if necessary.

For safety analyses, adverse events will be reported by treatment groups and by physiological systems as appropriate. Incidence of adverse events between treatments will be analyzed by CMH test. Changes in physical examinations will be displayed for each individual system. Net changes from pre-treatment laboratory test results and vital signs will be analyzed by descriptive statistics.

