Additionally, descriptive statistics will be provided for all of the endpoints. Frequency table will be provided for categorical data, while mean, standard deviation, maximum, minimum, median, inter-quartile range (IQR), and 95% two-sided confidence interval will be calculated for continuous measurements. In addition, endpoints of time to event will be presented by using the life table and Kaplan-Meier plot. The Kaplan-Meier estimates will also be provided for these time-to-event endpoints.

All treatment group comparisons will be conducted with significance level of 0.05.

SCHEDULE OF ASSESSMENTS

	Screening ¹	Initial ² Phase	Randomization ³ (Baseline)	Dosing/Observation								Follow-up			
	1	2	3	4	5	6	7	8	9	10	11 ¹¹	12	13	14	15
Week relative to Baseline visit	-3~-2	-2~0	0	1	2	3	4	6	8	10	12	14	16	20	24
Visit Window (days)	NA	±4	NA	±4	±4	±4	±4	±4	±4	±4	±4	±4	±4	±4	±4
Informed consent signed and given	X														
Screening number assignment	X														
Randomization			X												
Demographic data & medical history	X														
Inclusion and exclusion criteria	X		X												
Pregnancy test for applicable subjects	X										X				
Ulcer Evaluation ⁴	X		X	X	X	X	X	X	X	X	X	X	X	X	X
Vital signs	X		X	X	X	X	X	X	X	X	X	X	X	X	X
Physical examinations	X		X	X	X	X	X	X	X	X	X	X	X	X	X
Ankle Brachial Index ⁵	X														
Laboratory test: hemoglobin, hematocrit, RBC, platelet, WBC with differential counts, HbA1c, fasting glucose, AST, ALT, creatinine and BUN, albumin	X ⁶		X ⁷								X ⁸				
Record concomitant medication(s)	X	X	X	X	X	X	X	X	X	X	X	X	X	X	X
Standard of Care		X	X	X	X	X	X	X	X	X	X				
Record adverse events (AE) ⁹	X	X	X	X	X	X	X	X	X	X	X	X	X	X	X
Dispense trial medication			X	X	X	X	X	X	X	X					
Returned medication count				X	X	X	X	X	X	X	X				
Diary Dispensing			X												
Diary Return				X	X	X	X	X	X	X	X				
Complete exit form													X		X
Dismiss subject ¹⁰													X		X

Footnote:

- 1: Could be on the same day as the first day of Initial Phase or randomization visit if subject's Initial Phase can be waived
- 2: Can be waived if subject's diabetic foot ulcer(s) has been treated for at least 2 weeks, and is still eligible to enter this study
- 3: Could be on the same day as the last day of Initial Phase
- 4,10: Subjects with confirmed complete ulcer closure up will be arranged for ulcer evaluation for follow-up period; Subjects not with complete ulcer closure will take 4 weeks of safety evaluation

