3. STUDY POPULATION

3.1 Subjects Enrollment

The sample size is determined to be 80 versus 20 subjects (4:1 ratio) for Treatment versus Control groups, 100 subjects in total. To ensure the completion of 100 evaluable (= per-protocol) subjects, around 125 subjects will be recruited. All of the subjects will be recruited in Taiwan. Any subject fulfills all of the recruitment criteria will be screening and/or randomized into the study.

Re-screening for patient's eligibility will be allowed if the patient is willing to participate in the study and one of the following conditions meets:

1. If a patient consents to participate and meets the eligibility criteria but a delay occurs in starting to participate in due to certain change in situation such that some measurement relevant to eligibility became invalid owing to the delay
2. If the cause of screen failure has now resolved or adequately treated such that patient's medications have now stabilized

In these situations, if randomization has not occurred;

1. A new CRF will be used
2. A new Screening number will be assigned to the person
3. The person will be marked as having been re-screened on both the CRF and the site master list
4. The patient needs to sign a new ICF as part of the screening procedure.

It is not appropriate to re-screen a patient if he/she has previously failed to meet the eligibility criteria and no further changes or treatments have been able to indicate that the patient may be suitable.

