4.2 Randomization and Blinding

Permuted block randomization method will be applied to generate randomization codes. Each randomization number will be assigned to individual subject according to the time-sequence for screened subject becoming eligible.

Both CSTC1 and its matched vehicle will be prepared to be identical in all aspects to achieve the double-blind purposes. All subjects will take proper amount of CSTC1 or CSTC1 matched vehicle per application to ulcer area.

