10.2.3 Safety Analyses

[Redacted]

[Redacted]

[Redacted]

[Redacted]

[Redacted]

[Redacted]

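### Does testing adverse-event incidence by CMH under 4:1 allocation let a single vehicle event count as a significant safety advantage for CSTC1?

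*Combined protocol and SAP*

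**What the plan says.** The safety paragraph of the Protocol Summary (Statistical Analysis) has two consecutive statements on adverse events. The first concerns presentation: "adverse events will be reported by treatment groups and by physiological systems as appropriate". The second concerns inference: "Incidence of adverse events between treatments will be analyzed by CMH test". The listed safety endpoint (Protocol Summary and section 2.2.3) is the incidence of adverse events, with no subdivision by system. The summary closes its statistical part with a general level: "All treatment group comparisons will be conducted with significance level of 0.05".

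Safety is analysed on the ITT set, defined as "All randomized subjects who have received at least one dose study medication". Section 3.1 plans "80 versus 20 subjects (4:1 ratio) for Treatment versus Control groups" and expects to recruit around 125, which at 4:1 is about 100 on CSTC1 and 25 on vehicle. Section 4.2 adds: "Permuted block randomization method will be applied to generate randomization codes". It gives neither a block size nor whether blocks are kept within centre. The section that would hold the operative detail, "10.2.3 Safety Analyses", is entirely blacked out in the public version.

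**The concern.** The CMH statistic is referred to a chi-square distribution, and that approximation is poor when events are few and one arm is four times the other. A lone event falls on vehicle 20% of the time by chance, yet when it does, the uncorrected test calls it significant at 0.05. The mirror case, a lone event on CSTC1, gives p = 0.617, and at 100:25 it takes 14 events against none before an excess on CSTC1 reaches p < 0.05. The error would therefore run in one direction.

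If every physiological-system row carried such a p-value, a registration study could report some uncommon events as significantly rarer on CSTC1 on the strength of one vehicle subject. Safety is the secondary objective (section 2.1.2), so a reader who sees CMH, 4:1 and a blanket 0.05 level together has reason to look closer.

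**Working it through.** **Inputs.** From the documents: the CMH test, the 0.05 level, 80:20 planned, and about 100:25 from 125 recruited at 4:1. Assumed, because the documents give none: event rates, number of centres (5), and no continuity correction. The plan states no operating characteristic for this test, so there is no figure of its own to reproduce.

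**Single-event case.** With n1 on CSTC1, n0 on vehicle, N = n1 + n0 and m events in all, the one-stratum statistic is

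(a − n0·m/N)² / [n1·n0·m·(N − m) / (N²·(N − 1))],

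where a is the number of events on vehicle. For m = 1 and a = 1 the numerator is (n1/N)² and the variance is n1·n0/N², so the statistic equals n1/n0.

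- 80:20: expected 0.2, variance 0.16, statistic 0.64/0.16 = 4.00, p = 0.0455. Fisher p = 0.20.
- 100:25: the same, 4.00, p = 0.0455. Fisher p = 0.20.
- With a continuity correction, at either size: 0.3²/0.16 = 0.5625, p = 0.453.

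**How narrow the crossing is.** Significance needs n1/n0 above 3.8415, a vehicle share below 1/(1 + 3.8415) = 20.65%. The 4:1 design sits at 20%. At 99:26 the p-value is 0.051, at 79:21 it is 0.052, and at 96:25 it is 0.0500, just above the level.

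**Size of the uncorrected, unstratified test** (full enumeration of both binomials):

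| Split | 1% rate | 2% rate | 3% rate |
|---|---|---|---|
| 100:25 | 9.1% | 8.1% | 6.2% |
| 80:20 | 8.8% | 8.7% | 7.2% |
| 101:24 | 8.7% | 7.6% | 5.8% |
| 99:26 | 2.1% | 4.3% | 4.9% |
| 79:21 | 1.5% | 3.7% | 4.8% |

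Size exceeds 5% in this low range only for rates of about 0.3 to 3.8% at 100:25, or 0.35 to 4.65% at 80:20.

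**With centre strata** (simulation, 5 centres assumed, rates 1/2/3%): 9.1/8.1/6.2% if every centre is exactly 4:1, 5.7/5.9/4.9% with incomplete blocks within centre, and 4.4/4.9/4.5% if blocks are not kept within centre.

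**The comparison the text names.** Any-adverse-event incidence is not a rare-event category. At assumed rates of 20 to 50% and 100:25, the size of the CMH test is 4.6 to 5.0%, which is what a 0.05 test should give.

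**What an exact test would change.** At 100:25 and a 20% rate, Fisher's size is 3.6% against 4.6% for CMH. Power to detect more events on CSTC1 falls from 44% to 39% (20% vs 5%), from 85% to 83% (30% vs 5%) and from 52% to 43% (15% vs 1%). At rates of 1/2/3% Fisher's size is 1.0/1.6/1.7%, still all in CSTC1's favour: two vehicle events against none gives Fisher p = 0.039.

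**The case for a change.** The best case for the concern has four parts. Permuted blocks aim at 4:1, which is the split where the problem appears. If each of 100:25 randomized subjects goes undosed with an assumed probability of 2%, the ratio still stays above 3.84 in 91% of trials. The disagreement with the exact test is also not confined to one event: two on vehicle against one on CSTC1 gives CMH p = 0.042 and Fisher p = 0.10 at 100:25, and 0.048 against 0.11 at 99:26. Finally, the summary assigns laboratory and vital-sign changes to descriptive statistics, so a test for adverse events is a deliberate choice.

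All of this stands as a description of the uncorrected test on sparse rows. None of it shows that the plan runs the test on sparse rows. The visible wording separates reporting by system from testing incidence, and the second matches the listed endpoint. Choice of strata, continuity correction and tested categories are what a safety-analysis section would specify, and that section is redacted, so its silence cannot be counted against the plan. Nor is a switch to an exact test a plain correction. It gives up some power to detect harm and makes the overall comparison more conservative, while the false positives that remain at low rates still favour CSTC1. Statisticians can reasonably differ on that trade in a safety table.

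**Conclusion.** The concern does not hold. The p-value of 0.0455 and the sizes of 6 to 9% are correct, but they belong to an analysis the visible plan does not describe. On the natural reading, the CMH test is applied to overall adverse-event incidence, where its size is 4.6 to 5.0% at assumed rates of 20 to 50%.

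For the inflation to arise, five things must coincide: testing of individual categories, no continuity correction, no strata or strata that keep 4:1, a dosed ratio above 3.84, and true rates of roughly 0.3 to 3.8% at 100:25. The planned ratio of 4.0 meets the fourth only narrowly; the other four are not confirmed anywhere in the visible text. Even if all held, no visible decision rule uses an adverse-event p-value, efficacy conclusions rest on the ITT efficacy analysis, and the planned frequency tables would show one event against none beside any p-value.

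This conclusion rests on reading the summary's two sentences as reporting by system and testing overall. It would need another look only if the unredacted section 10.2.3 turned out to prescribe uncorrected CMH tests for each physiological system.

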- 5: The two blood pressures for calculating ABI, ankle and brachium, should be measured on the same side (left to left, right to right) and should be on the same side of target diabetic foot ulcer. However, the blood pressures of brachium may not be available for some patients. For such case, investigator is suggested trying to measure pressure of brachium of another side.
- 6: Test results within 14 days before Screening visit are acceptable; HbA1c test result within 28 days can be accepted. Albumin test will only be done at Screening and Randomization visits
- 7: Test results within 28 days before Randomization visit are acceptable
- 8: Test results within time window are allowed
- 9: AE should be recorded since informed consent is signed
- 11: For subject who has been confirmed complete closure before week-12 visit should be arranged for visit 11 assessment.

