4. STUDY DESIGN

This study is designed as a randomized, double-blind, vehicle-controlled, multiple center and parallel trial to evaluate the efficacy and safety of CSTC1 in patients with diabetic foot ulcer.

The potential subjects with diabetic foot ulcer at Screening visit will be arranged to enter an initial phase for 2 weeks in which subjects receive only standard of care, unless subject has receive any other regular therapy for at least 2 weeks. Subjects whose study ulcer size decreases by at least 30% during this initial standard-of-care phase or previous regular therapy period will be excluded from the study at investigator's discretion. The remaining eligible subjects will be randomly assigned to receive either one of topical application of CSTC1 dose or CSTC1 matched vehicle, 2 times daily.

The treatment duration for each subject is 12 weeks or up to confirmed complete ulcer closure, whichever comes first. That is, subjects will receive treatment for at most 12 weeks, which consists of 8 visits located at weeks 1, 2, 3, 4, 6, 8, 10, and 12. Subjects confirmed complete ulcer closure during treatment period will be arranged for a 12 week post-treatment follow-up. Subjects failed to achieve complete ulcer closure at week-12 visit will be arranged for 4 weeks of safety follow-up. Subjects happening to attain complete ulcer closure at week-12 visit will not receive further treatment but needs to be confirmed at week-14 visit. If confirmation of complete ulcer closure is reached at week-14 visit, the subject will continue the post-treatment follow-up visit until week-24 visit. Otherwise, the subject will be arranged for safety follow-up until week-16 visit.

After the treatment period, the post-treatment follow-up period for subjects confirmed complete ulcer closure will consist of 4 visits at weeks 2, 4, 8, 12 after confirmation of complete ulcer closure. The safety follow-up period for subjects failed to achieve complete ulcer closure at week-12 visit will consist of 2 visits at weeks 14 and 16.

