7.5 Follow-up visits

The follow-up visits will be performed at 2, 4, and 8 weeks after for subjects achieving confirmed complete ulcer closure during treatment period and at 2 weeks after treatment period (week 14 or visit 12) only for those not.

(The visit day will be week 14 for visit 12, week 16 for visit 13, and week 20 for visit 14, each with time window ± 4 .)

1. Ulcer evaluation
2. Vital signs
3. Perform physical examinations
4. Record changes on concomitant medication(s)
5. Record adverse event(s)

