8.3 Collecting, Recording and Reporting of Adverse Events

8.3.1 Collecting and Recording of AE

AEs may be volunteered spontaneously by the study subject, discovered as a result of general questioning by the study staff, or determined by physical examination. All AEs starting from signing ICF will be recorded on the CRF. For all AEs, the investigator must pursue and obtain adequate information both to determine the outcome of the AE and to assess whether it meets the criteria for classification as a serious AE requiring immediate notification. Follow-up of the AE, even after the date of study drug discontinuation, is required if the AE persists. The study subject will be followed until the event resolves or stabilizes at a level acceptable to the investigator. For patients receiving hemodialysis, taking regular arteriovenous fistula will not be considered as an AE.

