10.2 Statistical and Analytical Plans

10.2.1 Analysis Population

Three data sets will be introduced for statistical analysis.

Intent-to-treat (ITT) population:

- All randomized subjects who have received at least one dose study medication.

Per-protocol (PP) population:

- A subset of ITT population
- Fulfill all inclusion and exclusion criteria
- Dosed with at least 8 weeks study drug or with early confirmed complete ulcer closure AND with at least 70% treatment compliance
- Did not receive any prohibited treatment during treatment period
- With any post-treatment assessment relevant to efficacy endpoint up to end of dosing period

Efficacy endpoints will be analyzed on ITT and PP population. Demographics, baseline characteristics, and safety endpoints will be analyzed on ITT population. The conclusion of efficacy will be made according to the results of ITT population analysis.

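### AE incidence is tested between arms with no stated common window, although length of AE follow-up depends on ulcer closure

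*Combined protocol and SAP*

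**What the plan says.** The safety paragraph of the Protocol Summary (Statistical Analysis) reads: "Incidence of adverse events between treatments will be analyzed by CMH test". The Summary adds that "All treatment group comparisons will be conducted with significance level of 0.05", and Section 10.2.1 says that "safety endpoints will be analyzed on ITT population", meaning randomized subjects with at least one dose. No visible text gives an AE window, a treatment-emergent definition or an exposure-adjusted rate. Section 10.2.3 (Safety Analyses) is redacted.

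AE recording starts at consent. Footnote 9 of the Schedule of Assessments says "AE should be recorded since informed consent is signed", and Section 8.3.1 says "All AEs starting from signing ICF will be recorded on the CRF". Sections 7.5 and 7.6 include AE recording at each follow-up visit and at the final visit.

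The end of recording depends on the ulcer. Section 4 says "Subjects failed to achieve complete ulcer closure at week-12 visit will be arranged for 4 weeks of safety follow-up", which ends at week 16. For subjects with confirmed closure there are two clocks:
- **From confirmation.** Sections 4 and 7.6 count 12 weeks from confirmation.
- **Fixed weeks.** The Schedule of Assessments places the follow-up visits at weeks 14, 16, 20 and 24. Section 7.5 gives fixed weeks for visits 12 to 14, although its opening sentence counts from closure.

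For closure first seen at week 12 and confirmed at week 14, Section 4 says "the subject will continue the post-treatment follow-up visit until week-24 visit".

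**The concern.** Closure is the primary efficacy outcome and the thing that treatment is meant to change. It also decides how long a subject is watched for AEs. A comparison of the proportion with any AE, taken over each subject's whole follow-up, gives more time to accumulate events to the arm with more closures. Much of that added time is after study treatment has stopped.

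Safety is the secondary objective, and Section 2.1.2 says that the study is for registration. A difference in AE incidence that partly reflects follow-up length would be hard to interpret in a dossier. With equal AE risk per week, it would count against CSTC1 if CSTC1 heals more ulcers, and in its favour if it heals fewer.

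**Working it through.** The plan gives no figure on this point to reproduce. Closure rates and AE hazards below are assumptions, and ranges are shown.

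**Step 1: end of AE observation.** Subjects without closure: week 16. Subjects with confirmed closure:

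| Confirmed at week | 3 | 4 | 6 | 8 | 10 | 12 | 14 |
|---|---|---|---|---|---|---|---|
| Confirmation clock, last week | 15 | 16 | 18 | 20 | 22 | 24 | 24 (Section 4; 26 by adding 12) |
| Fixed clock, last week | 24 | 24 | 24 | 24 | 24 | 24 | 24 |

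Confirmation at week 3 pairs weeks 1 and 3, with the week 2 visit between them. If the two visits must be adjacent and 2 weeks apart, the first possible pair is weeks 4 and 6, and every closed ulcer is followed to at least week 18.

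**Step 2: fixed clock, equal AE hazard h per week for everyone.** The risk of any AE by week t is 1 - exp(-ht). With closure proportions pT and pC, the expected difference is

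(pT - pC) x [exp(-16h) - exp(-24h)].

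- Mean follow-up at 60% vs 30% closure: 0.6 x 24 + 0.4 x 16 = 20.8 weeks, against 0.3 x 24 + 0.7 x 16 = 18.4 weeks, which is 13% more.
- h = 0.01: 0.3 x (0.8521 - 0.7866) = 2.0 points.
- h = 0.03: 0.3 x (0.6188 - 0.4868) = 4.0 points.
- At 70% vs 30% closure the multiplier is 0.4, giving 2.6 to 5.3 points.

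**Step 3: confirmation clock, equal hazard.** Closure times are exponential with rate -ln(1 - p)/12, first seen at weeks 1, 2, 3, 4, 6, 8, 10 or 12. Confirmation is taken as 2 weeks later, and follow-up ends 12 weeks after that, at week 24 at the latest. Mean follow-up at 60% vs 30% is 18.2 vs 17.3 weeks, and the excess is 0.8 to 1.6 points for h = 0.01 to 0.03.

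**Step 4: AE hazard falls after treatment stops for closure.** Subjects with closure have hazard h until confirmation (week 12 at the latest) and f x h afterwards. Subjects without closure keep h to week 16. At 60% vs 30% closure and h = 0.01 to 0.03:
- f = 0.7: -0.1 to -0.3 points on the confirmation clock; still positive, +0.7 to +1.6, on the fixed clock.
- f = 0.5: about -0.1 to -0.25 points on the fixed clock.

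**Step 5: size against the noise.** The standard error of an AE difference is sqrt[p(1 - p)(1/n1 + 1/n2)].
- 80 vs 20: sqrt(0.16 x 0.0625) = 10.0 points at 20% risk; sqrt(0.25 x 0.0625) = 12.5 points at 50%.
- 100 vs 25 (125 recruited at 4:1): sqrt(0.16 x 0.05) = 8.9 points; sqrt(0.25 x 0.05) = 11.2 points.

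**Step 6: effect on the test.** Exact rejection rates of an unstratified Mantel-Haenszel test, 100 vs 25, two-sided 0.05 (the sidedness is assumed), fixed clock, equal hazards:
- Closure 50% vs 30%, 16-week AE risk 20% to 60%: 4.6% to 6.1%.
- Closure 60% vs 20%, 16-week AE risk 60%, the most extreme case tried: 9.2%, against 4.9% with no spurious difference. Rejection towards more AEs on CSTC1 is 8.6% against 2.6%. The spurious difference here is 5.9 points.

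**The case against.** **The operative section cannot be seen.** Section 10.2.3 is redacted, and an AE window or exposure adjustment would normally stand there. A reader might infer that the plan has none; the documents do not support that. What stands is that the Summary states the comparison without qualification.

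**The direction is not fixed.** A reader might infer that the better-healing arm must collect extra AEs. That needs about the same AE hazard in someone with a healed ulcer and no study cream as in someone with an open, treated ulcer. The documents give no rates, and step 4 shows the sign turning. Nor is every closed ulcer necessarily followed for longer: confirmation at week 3, if allowed, ends at week 15 on the confirmation clock.

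**CMH does not itself require equal observation time.** If treatment affects neither closure nor AEs, follow-up has the same distribution in both arms and the test is valid. The difficulty arises only when closure differs.

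**The effect is small.** This stands. On the confirmation clock it is 0.8 to 1.6 points in the main scenario, and no visible decision rule hangs on the p-value.

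**The remedy is partial.** This also stands. Section 4.1 says that the 12-week follow-up serves partly to monitor adverse effects on surrounding tissue, and the proposed window takes those late events out of the between-arm test. It also leaves time on treatment unequal: 9.4 vs 10.9 weeks on average in the 60% vs 30% model.

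**Conclusion.** The point holds in a limited, conditional form. On the visible text, length of AE observation depends on the efficacy outcome, and the Summary compares AE incidence without naming a common window. If closure differs between arms, the result mixes safety with follow-up time.

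Under equal hazards of 1-3% per week and 60% vs 30% closure, the artefact is about 1 to 4 points, and it reaches about 5 at 70% vs 30% on the fixed clock. These closure rates, hazards and the constant-hazard form are assumptions. If risk falls after closure, the difference is smaller or slightly reversed. In every main scenario it is well below one standard error, and the test's error rate moves noticeably only in extreme cases. The case for acting is that the dependence is systematic and nearly free to remove.

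**What to change.** 1. If Section 10.2.3 already defines an AE window or exposure adjustment, repeat it in the Protocol Summary. Steps 2 and 3 are then unnecessary.
2. Otherwise, base the CMH comparison on AEs with onset from first application to week 16. Tabulate AEs between consent and first application, and AEs after week 16, separately by arm and without a test.
3. Add exposure-adjusted AE rates (events per subject-week of observation) by arm.
4. Reconcile the confirmation-based follow-up in Sections 4 and 7.6 with the fixed weeks in the Schedule of Assessments and Section 7.5. Until that is done, it is not certain that every subject with early closure is scheduled to reach week 16.

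When everyone is observed over the whole window, the spurious difference under equal hazards is zero, and the rejection rate in the calculation above returns to about 4.6% to 5.1%.

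The cost is a few sentences of analysis text and one extra AE table, with no new data. Late AEs leave the between-arm test but are still reported. The window does not equalise time on treatment, and the text should say so.
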